1.1.2 Fluoroscopy related health risks and occupational injuries

Historically, fluoroscopy has been the standard for guiding EP interventions; however, despite advancements that have reduced radiation exposure to safer levels⁷⁻¹⁰, the need for heavy personal protective equipment (PPE) remains a significant concern. Prolonged use of leaded PPE has been linked to chronic occupational injuries such as back, neck, and other joint pain, as well as more serious conditions like spinal disc herniation^{11, 12}. These injuries are particularly concerning for healthcare providers who perform complex and lengthy procedures, potentially limiting their career longevity^{13, 14}.

1.1.3 Financial and environmental burdens of fluoroscopic labs

Traditional EP labs pose substantial financial and environmental burdens. The setup of a new fluoroscopic lab, particularly one using DSA systems, involves significant initial investments—typically between 5 to 8 million yuan (¥) (687,400 to 1,100,000 dollars) per lab. Maintenance costs are also high, with annual fees reaching into the hundreds of thousands of yuan (¥) per lab. Moreover, fluoroscopic systems consume considerable energy, with each procedure requiring 60 to 70 kilowatt-hours of electricity to power X-ray machines and cooling systems. This not only drives up operational expenses but also contributes to increased carbon emissions. The sustainability of this approach is increasingly being questioned.

1.1.4 Fluoro-less/-free practices for AF catheter ablation

Non-fluoroscopic EP labs offer a feasible alternative, relying on advanced technologies such as three-dimensional (3D) mapping systems, contact-force catheters, and intracardiac echocardiography (ICE) to guide PE procedure without need for fluoroscopy. These systems not only reduce the need for heavy PPE and radiation exposure but also lower the financial and energy costs associated with traditional EP labs, making them more accessible and sustainable. Non-fluoroscopic EP labs offer a scalable and cost-effective solution, providing a more practical approach to addressing the growing demand for ablation therapies. Non-fluoroscopic EP labs, which eliminate the need for fluoroscopic imaging, have proven to be both feasible and safe¹⁵⁻²⁰. The shift away from radiation-based guidance aligns with a growing focus on minimizing procedural risks and optimizing patient outcomes^{21, 22}. While early studies suggest that non-fluoroscopic ablation techniques are feasible and effective²³⁻²⁵, comprehensive data on their clinical outcomes and long-term safety are still limited. There remains a critical need for large-scale, standardized assessments to validate these findings and support broader adoption of the technology²⁶. Furthermore, recent studies have suggested that the characteristics of the blanking period following PFA may differ from those after conventional RF ablation, as early recurrences of atrial arrhythmias do not necessarily predict long-term failure, and the blanking period may be substantially shorter than the traditional 3-month duration.^{4, 27, 28} This highlights the need for large-scale studies to assess the real-world performance of non-fluoroscopic ablation techniques.

1.2 What are the principal research questions to be addressed?

1.2.1 Study Question and Hypothesis

We seek to assess the **efficacy** and **safety** of catheter ablation procedures for the treatment of AF, performed in a non-fluoroscopic EP lab. We hypothesize that the efficacy and safety outcomes of AF ablation in patients meeting the inclusion criteria of non-fluoroscopic EP lab will be non-inferior to those

achieved in a conventional DSA lab under identical technical conditions. The findings of this study will not only validate the feasibility of non-fluoroscopic EP labs for AF ablation but also provide a foundation for their application to emerging ablation technologies, such as pulsed field ablation (PFA), which are anticipated to gain widespread adoption in the near future.

1.2.2 Principal Research Questions

- (i) **Efficacy:** Do patients undergoing catheter ablation for AF in a non-fluoroscopic EP lab achieve comparable success rates after one year or more of follow-up as those treated in a traditional DSA lab?
- (ii) **Safety:** Are severe complication rates in a non-fluoroscopic lab non-inferior to those in a traditional DSA lab?
- (iii) **Cost-effectiveness:** Is a catheter ablation strategy in a non-fluoroscopic EP lab cost-effective compared to traditional approaches?
- (iv) **Target Population Selection:** Given that not all patients are suitable for treatment in a non-fluoroscopic EP lab, can we identify specific patient characteristics at the point of entry to determine suitability for non-fluoroscopic procedures?

2 Description Of Study Device

The following devices are included in the trial. New devices could be added to the list if they become available in the future.

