Efficacy and Safety of Catheter Ablation for Atrial Fibrillation in Non-fluoroscopic
Cardiac Electrophysiology Lab:
A Non-Inferior, Multi-Center, Prospective Randomized Controlled Trial
(NCT06719921)

Protocol

Version V3.0

11/27/2025

PROTOCOL SYNOPSIS

Title	Efficacy and Safety of Catheter Ablation for Atrial Fibrillation in Non-Fluoroscopic Cardiac Electrophysiology Lab: A Non-Inferior, Multi-Center, Prospective Randomized Controlled Trial
Purpose	A randomized controlled trial to investigate whether catheter ablation in a non-fluoroscopy lab is non-inferior to catheter ablation in a conventional DSA lab in terms of efficacy and safety for treating atrial fibrillation (AF).
Principal Investigator	[name]
Coordinating Center	Sir Run Run Shaw Hospital serves as the coordinating center for this clinical study with 16 EP centers participating.
Trial Sponsor	Biosense Webster
Number of Subjects	Up to 724 patients (procedures) will be enrolled over 1 year at 16 EP centers.
Inclusion Criteria	
Subjects must meet all the following inclusion criteria to be eligible for participation in this trial.
 
 • Age: ≥ 18 years • Patients diagnosed with paroxysmal AF or persistent AF ≤ 1 year, who are referred for catheter ablation. • Patients referred for catheter ablation of AF (Pulmonary Vein Isolation) as a first-time intervention (no prior catheter ablation or surgical procedures for AF). • The patient is able and willing to provide written informed consent

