2) Safety endpoints will be collected in details and analyzed for comparison between the groups, but they will not be used to determine the sample size.

Flowchart

Ablation Procedure details (study and control group)

The study will target AF catheter ablation procedures (Pulmonary Vein Isolation). After obtaining written informed consent, eligible patients will be randomized into one of the following two groups:

Group 1: Non-Fluoroscopic Lab Group

1. Ablation procedures will be performed in a catheterization lab equipped with non-fluoroscopic 3D electroanatomic mapping systems.
2. No routine fluoroscopy will be used, except if deemed necessary for safety (e.g., complications or unexpected procedural difficulties), adhering to the ALARA principle.
3. Pulmonary vein isolation (PVI) will be the sole ablation strategy, following the study protocol.

Group 2: Fluoroscopic Lab Group (DSA Lab)

1. Ablation procedures will be conducted in a fluoroscopy-guided catheterization lab using digital subtraction angiography (DSA) for catheter navigation.
2. Radiation exposure will be recorded, and efforts will be made to minimize exposure by following the ALARA principle.
3. Similar to Group 1, PVI will be the sole ablation strategy, as per protocol.

Ablation strategy

The primary ablation strategy for both groups will be pulmonary vein isolation (PVI).

Other additional ablation, including but not limited to linear ablation, complex fractionated atrial electrogram (CFAE) ablation, or superior vena cava (SVC) isolation is not recommended unless necessitated by one of the following:

- Documented atrial flutter (AFL) or atrial tachycardia (AT) observed during the procedure, or
- Arrhythmias originating from the specific region requiring intervention.

Energy Selection Principles

Energy modality (RF or PF) will be selected by the investigator prior to randomization according to routine clinical practice, with a population-level expectation that the proportion of PFA among newly enrolled patients will progressively increase to approximately 50–60%, without influencing individual clinical decision-making.

Recommendations

- 1) The configuration of the Non-fluoroscopic Lab needs to be in accordance with the latest expert consensus

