3.2 Study Rationale and Objective

This randomized controlled trial aims to evaluate the **efficacy, peri-procedural safety, and clinical outcomes** of catheter ablation performed in non-fluoroscopic EP labs compared to procedures in conventional DSA lab.

With the rapid adoption of non-fluoroscopic EP labs in China, it is essential to assess their performance to ensure safe and effective care. We hypothesize that non-fluoroscopic procedures will demonstrate non-inferior safety and efficacy to fluoroscopy-guided ablations, while offering benefits such as reduced costs, minimized radiation exposure for physicians, and improved environmental sustainability.

This study will provide evidence to guide clinical practice, improve patient care, and support the broader adoption of non-fluoroscopic EP technologies, enhancing access to advanced arrhythmia treatments and optimizing outcomes for patients with AF.

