3.4 Study Endpoints

3.4.1 Primary endpoints

The primary efficacy endpoint is freedom from any documented atrial arrhythmia, including AF, atrial tachycardia or atrial flutter episodes lasting longer than 30 seconds without antiarrhythmic drugs, for 12 months after the index ablation procedure, excluding a 3-month blanking period. The continuation or reinitiation of class I or class III antiarrhythmic drugs after the 3-month post ablation blanking period, as well as electric cardioversion or catheter ablation for any atrial arrhythmias, are considered treatment failures for the primary end point.

The primary safety endpoint is a composite of the following prespecified procedure-related serious adverse events:

- Major vascular complication or major bleeding within the first 7 days post procedure.
- Development of a clinically significant pericardial effusion.
- Transient ischemic attack.
- Stroke.
- Myocardial infarction.
- Severe pulmonary vein stenosis.
- Atrial-esophageal fistula, or phrenic nerve injury within 3 months.
- Death.

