3.5 Sample Size

For **efficacy** as the primary endpoint, sample-size was calculated by non-inferiority log-rank test with 1:1 design. The expected recurrence rate of AF is 30% for control group based on previous studies and our experience, and a hazard ratio of 1.3 was used for establish non-inferiority. Based on a power of 80% and an alpha of 0.05, proportion lost to follow up 5%, a sample size of **724 patients (362 for each group)** was estimated.

Safety endpoints will still be collected in detail and analyzed for comparison between the groups, but they will not be used to determine the sample size.

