3.8 Clinical Equipoise

3.8.1 Sample Size Justification

Since complication rates are very low (estimated at 2-3% in the ICE group, based on literature²⁹⁻³² and our prior experience), conducting a controlled study focusing on safety endpoints is not feasible. Additionally, our previous registry study has already provided supporting evidence on safety. In this study, while safety endpoints will still be collected in detail and compared between the two groups, they will not be used to calculate the sample size. Instead, the sample size calculation will be based on the primary efficacy endpoint.

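### Non-inferior safety is stated as purpose, hypothesis and principal question, but N is not set by safety and 724 patients cannot usefully support that claim

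*Protocol*

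**What the plan says.** The safety claim appears in four places in the Protocol.

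- Synopsis, Purpose: to investigate whether ablation in a non-fluoroscopy lab is "non-inferior to catheter ablation in a conventional DSA lab in terms of efficacy and safety".
- Section 1.2.1: the hypothesis is that "the efficacy and safety outcomes of AF ablation in patients meeting the inclusion criteria of non-fluoroscopic EP lab will be non-inferior".
- Section 1.2.2(ii): "Are severe complication rates in a non-fluoroscopic lab non-inferior to those in a traditional DSA lab".
- Section 3.2: the hypothesis is that "non-fluoroscopic procedures will demonstrate non-inferior safety and efficacy to fluoroscopy-guided ablations".

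The endpoint has matching rank. In section 3.4.1, "The primary safety endpoint is a composite of the following prespecified procedure-related serious adverse events"; the synopsis lists it as primary too.

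Other sections set a lower ambition. The synopsis says that "Safety endpoints will be collected in details and analyzed for comparison between the groups", and section 3.5 adds that "they will not be used to determine the sample size". Section 3.8.1 gives the reason: complications are estimated at 2-3% in the ICE group, so that "conducting a controlled study focusing on safety endpoints is not feasible". It also points to an earlier registry as supporting safety evidence. The one margin in the protocol, a hazard ratio of 1.3, belongs to the efficacy log-rank test (synopsis and section 3.5). Section 8 lists chi-square or Fisher's exact tests for categorical variables in general.

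**The concern.** Two parts of the same document ask different things of the same data. One part promises a conclusion that safety is non-inferior. The other explains why a trial of this kind cannot be built around safety, and fixes N without it.

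This matters because section 3.2 expects the results to guide practice and support wider adoption of these labs. A primary safety result from a couple of dozen events or fewer would be reported under a stated non-inferiority aim. If the interval is too wide to exclude a large increase in risk, that wording promises more than the trial can deliver, whichever margin or test is written down later.

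**Working it through.** **The protocol's own N.** Inputs from section 3.5 and the software output in the synopsis: HR margin 1.3, true HR 1.0, alpha 0.05, power 80%, reference hazard 0.30, accrual 1 and total time 3 (read as years), loss 0.05 (taken here as a yearly hazard), 1:1 allocation.

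- Events: 4(z0.95 + z0.80)² / (ln 1.3)² = 4(1.645 + 0.842)² / 0.0688 ≈ 360.
- Event probability: (0.30/0.35) × [1 − (e^−0.70 − e^−1.05)/0.35] = 0.498.
- N = 360 / 0.498 = 723, matching the output's 723 and the stated 724.
- With two-sided 0.05, N would be 918. So the stated N corresponds to one-sided 0.05.

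Nothing in this calculation involves safety. Whether its time inputs suit the efficacy endpoint is a separate matter.

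**What 362 per arm gives for safety.** Assumption: the 2-3% in section 3.8.1 is the true rate p of the composite in both arms. ICE is required in both arms (section 3.7), but the protocol gives no rate for the composite itself. Margins are also assumed, since none is stated.

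- Expected total events, 724 × p: 14.5, 18.1 and 21.7 at p = 2%, 2.5% and 3%.
- 95% half-width of the risk difference, 1.96 × √(2p(1 − p)/362): 2.04, 2.27 and 2.49 points.

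Power of the Farrington-Manning score test for the risk difference, by exact binomial enumeration with equal true rates:

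| Margin | One-sided alpha | p = 2% | p = 2.5% | p = 3% |
|---|---|---|---|---|
| 2 points | 0.05 | 56% | 50% | 45% |
| 2 points | 0.025 | 42% | 36% | 32% |
| 3 points | 0.05 | 84% | 78% | 73% |
| 3 points | 0.025 | 75% | 67% | 60% |

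Smallest margin m with at least 80% power (0.01-point grid), and the risk ratio (p + m)/p that it tolerates:

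| One-sided alpha | p = 2% | p = 2.5% | p = 3% |
|---|---|---|---|
| 0.05 | 2.76 points (2.38-fold) | 3.04 (2.22-fold) | 3.28 (2.09-fold) |
| 0.025 | 3.20 points (2.60-fold) | 3.52 (2.41-fold) | 3.79 (2.26-fold) |

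The simpler unpooled-variance formula gives slightly smaller margins, 2.6-3.2 points at one-sided 0.05 and 2.9-3.6 at 0.025, with the same message.

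**If the generic test in section 8 were applied.** Exact power of the uncorrected chi-square test (two-sided 0.05) to detect a true doubling, p against 2p, is 35%, 43% and 50% at p = 2%, 2.5% and 3%. Even with doubled risk, a non-significant result would occur about half the time or more.

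**The case against.** The strongest reply has four parts.

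- **An analysis plan may hold the margin and the test.** This stands. Their absence from the protocol is not the finding. A reader might infer that the trial has no criterion at all for the safety claim, but the protocol alone cannot show that. What an analysis plan cannot do is narrow the interval from 724 patients.
- **Section 8 is one generic paragraph.** This also stands. It does not repeat even the efficacy non-inferiority test, so it is not a full list of methods. A reader might infer that P>0.05 will be taken as proof of non-inferior safety. The protocol does not say so, and the chi-square power above matters only if someone reads the result that way.
- **The sizing choice is open.** It is stated in the synopsis, 3.5 and 3.8.1. Section 3.8.1 can be read simply as explaining why safety does not set N, and no text makes trial success depend on safety. So there is no concealment and no fault in the sizing. But disclosure explains N; it does not support a non-inferiority claim drawn from it.
- **The sizes rest on assumptions.** True: the protocol gives neither a composite rate nor a safety margin. At one-sided 0.05 a 3-point margin has 73-84% power, so the data are not uninformative for every margin. Whether 3 points is acceptable is a clinical judgement that the documents do not settle, but on an assumed 2-3% rate it means accepting a rate of 5-6%.

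**Conclusion.** The point holds in a limited form. Non-inferior safety is written as purpose, hypothesis and principal question with a primary endpoint behind it, while the protocol's own reasoning says a safety-focused controlled comparison is out of reach and N ignores safety. If the composite occurs in 2-3% of both arms, only a margin equal to or larger than the expected rate itself reaches 80% power. A 2-point margin has 45-56% power at one-sided 0.05, the reading that reproduces the protocol's N, or 32-42% at one-sided 0.025.

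This is a mismatch between claim and precision, not an error in the sample size. It should be fixed, but it leaves randomization, data collection and the efficacy comparison untouched.

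**What to change.** In the synopsis Purpose and sections 1.2.1, 1.2.2(ii) and 3.2, limit the non-inferiority claim to efficacy. Keep the composite as the primary safety outcome, for estimation: the rate in each arm and the risk difference with a 95% score confidence interval. Add one sentence that a non-significant difference will not be read as non-inferior safety. This follows the reasoning already in section 3.8.1.

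If the sponsor prefers to keep the claim, the protocol should justify a risk-difference margin, state the decision rule with its one-sided alpha, and report the power at N = 724. From the figures above, a margin with about 80% power would be roughly 3-4 points, which may be hard to defend against a 2-3% rate.

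The preferred route costs a more modest safety claim and a written amendment with IRB/EC approval (section 5.2). It consists of four wording edits and the added estimation text, with no new patients or data.

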2.1 CARTO® 3 System

The CARTO® 3 System is an imaging platform designed to support precise catheter navigation during cardiac procedures by generating real-time, three-dimensional maps of the heart. Utilizing electromagnetic technology, it provides accurate location and orientation of catheters, contributing to enhanced procedural safety and efficiency. The system employs magnetic sensors embedded in the catheters, along with six patient patches, to calculate catheter positioning based on electromagnetic signals. Fast Anatomical Mapping (FAM) enables the rapid creation of detailed heart maps, streamlining the mapping process and improving workflow.

2.2 SOUNDSTAR® Intracardiac Echocardiography (ICE)

ICE catheters are **8 or 10 Fr steerable phased-array devices** that provide a **90° ultrasound sector** perpendicular to the catheter tip. The catheter tip can be deflected **up to 160° in two planes** (anteroposterior and lateral), enabling four-directional movement (anterior, posterior, left, and right) to generate diverse **2D imaging**.

The CARTOSOUND® Module is a new software module that integrating real-time 3D ultrasound imaging with the CARTO® 3 System, enhancing

visualization of soft tissue during cardiac procedures. The SOUNDSTAR® catheter, equipped with a **navigation sensor**, allows its tip to be visualized on CARTO maps. This additional imaging capability allows for better catheter placement and monitoring of potential complications, such as blood clots or fluid accumulation. By improving visualization of critical structures, including the esophagus, the module helps minimize risks associated with catheter ablation procedures.

2.3 Thermocool Smarttouch® & Thermocool Smarttouch® SF (ST&STSF) Catheter

ST catheter is an irrigated-tip ablation, contact-force (CF)-sensing catheter indicated for cardiac mapping and ablation. The catheter contains a porous tip with 6 holes at the distal end. STSF catheter is a newer generation of the CF-sensing and irrigated-tip ablation catheter indicated for cardiac mapping and ablation. The catheter contains a porous tip with 56 holes at the distal end. The increased number of holes at the distal tip improves the cooling effect at the catheter-tissue interface. This newer design also requires less fluid delivery through the distal tip which could reduce the risk of volume overload. When used in conjunction with the Carto®3 system, the catheter of both kinds is able to provide real-time CF data during catheter ablation. Due to the product's indication restrictions, we suggest to use ST/STSF catheter for persistent AF patients.

SURPOINT is another new software module running with Carto 3 system. When used with ST and STSF catheter, SURPOINT is able to display AI value real-time on the Carto 3 system. The AI values can be used to guide the catheter ablation for durable lesion creation by ST and STSF catheter.

2.4 QDOT catheter

The Biosense Webster QDOT MICRO™ Catheter is a steerable multi-electrode luminal catheter with a deflectable tip designed to facilitate electrophysiological mapping of the heart and to transmit radiofrequency (RF) current to the catheter tip electrode for ablation purposes. The catheter contains force-sensing technology that provides a real-time measurement of contact force between the catheter tip and the heart wall. The location sensor embedded in the tip section transmits location and contact force information to the CARTO® 3 System.

The catheter incorporates six thermocouple temperature sensors in the tip section that can accurately monitor the catheter-tissue interface temperature and tip stability.

2.5 Varipulse Platform

The VaripulseTM platform from Biosense Webster is an innovative pulsed field ablation (PFA) system designed for treating atrial fibrillation. It uses a 7.5Fr circular catheter with 10 electrodes, each with its own irrigation pore to

improve cooling during ablation. The catheter is highly flexible, with 180° deflection in one direction and 90° in the other, making it easier to reach all pulmonary veins, including the more difficult-to-access right inferior pulmonary vein (RIPV).

The PFA energy is delivered in a bipolar pattern between alternating electrodes (e.g., between electrodes 1 and 3), as well as between adjacent pairs (e.g., electrodes 1–2 and 2–3). The system applies 1800V of pulsed energy through brief microsecond-long pulses, lasting a total of 250 microseconds per application.

During the procedure, irrigation is maintained at a flow rate both at rest and during ablation, to ensure safe and effective procedure.

